3.7.2 Adverse Events

The frequencies of adverse events, serious adverse events and device deficiencies will be reported in summary tables. These tables will show the number of subjects per group presenting a (serious) adverse event and the incidence of its occurrence.

Tabulations will be provided for system organ class and stratified by relation to the investigational product. Any withdrawals from the study due to adverse events will be reported. All measures taken due to adverse events will be reported.

AEs of special interest

- Number of patients with pancreatitis
- Number of patients with bleeding
- Number of patients with perforation
- Number of patients with complications associated with sedation/anesthesia
- Number of patients with other complications

For pre-treatment events summary tables and listings will be provided.

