1.2 Justification for the Design of the Clinical Investigation

Deep enteroscopy is well established with Balloon assisted enteroscopy procedures, however there is a need for innovative and faster methods, less resource utilization which at the same time provide more comfort for the patients.

Currently available and published data for PowerSpiral was collected by means of Investigator Initiated Trials (Mans et al. 2018; Neuhaus et al. 2016; Beyna et al. 2018; Beyna 2018). With this Olympus sponsored Registry further data about performance and safety for this new medical device will be collected in a larger patient population. Obtained safety data will be compared to data published in respective guidelines or literature.

This study will be performed in parallel to the European market launch of this new medical device. It is a registry study with a CE marked medical device whose application within the intended use will be captured. The registry and does not impose any additional procedure or risk to the patient as we strive to document daily clinical routine. Therefor this study is observational (non-interventional) in nature.

For the same reason inclusion criteria are kept as broad as possible. In summary all patients are eligible where the physician realizes an indication for deep enteroscopy for further diagnostic or therapeutic work up. The exclusion criteria will only affect patients under the age of 18 years and pregnant women. Otherwise clinical judgement of the treating physician is the only relevant and leading reason for exclusion. Of course giving signed informed consent by all study subjects is a prerequisite for participation in this "registry".

For this study approximately 12 European sites will be recruited that offer deep enteroscopy to their patients. This international multi-center setup will give a more representative picture and avoid a single-site bias. Furthermore enrollment will be completed earlier compared to a single center approach.

The prevailing complications of a deep enteroscopy are pancreatitis, perforation, bleeding and adverse events associated with sedation or anesthesia (Aktas et al. 2010; Akarsu et al. 2014; Akerman and Cantero 2009; Arulanandan et al. 2016; He et al. 2013; Moeschler and Mueller 2015). Generally these are independent if the procedure was performed as a diagnostic or therapeutic procedure however the complications rate is usually higher in interventional cases (Rondonotti et al. 2018).

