4.1.3 Safety evaluation

The following safety variables will be collected:

- Serious adverse events during and after enteroscopy procedure
- Serious adverse events (procedure or product related)
- Adverse events during enteroscopy procedure

The safety variables will be tabulated for all study participants.

Adverse events data will be processed in the statistical analysis after coding.

AEs and device deficiencies will be presented in summary tables. These tables will show the number of subjects per group presenting an adverse event and the incidence of its occurrence. Adverse events will be grouped by system organ class and stratified by severity (mild, moderate, severe) and by relation to study treatment (unrelated or related according to the categories definite, probable and possible).

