11.3 Reporting Responsibilities

11.3.1 Serious Adverse Events (SAE) / Serious Adverse Device Effects (SADE)

After the signature on the consent form is obtained, any SAE occurring while the subject is enrolled in the study must be immediately reported by the investigator.

Clinical Investigation Plan

CIP Reference No.:2018-GI (OEKG) -01. The **SAMISEN** study - Final Version 02 - Date 23th April 2019

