3.1 Populations for Analysis

All patients who did not undergo at least one enteroscopy will be considered as dropouts. Dropouts will be excluded from any statistical analyses.

Four different analysis populations will be defined:

The **core safety population (cSAF)** will consist of all patients who underwent at least one enteroscopy. Training patients will not be part of the cSAF.

The **general safety population (SAF)** will consist of all patients who underwent at least one enteroscopy including the training patients.

The **core intent-to-treat population (cITT)** will include all patients who underwent at least one enteroscopy and did not have any major protocol deviations. Training patients will not be part of the cITT.

The **general ITT population (ITT)** will comprise all patients who underwent at least one enteroscopy and did not have any major protocol deviation including the training patients.

Only patients of part A are covered by this SAP. For the analysis of data from patients of part B (ERCP patients), a separate SAP will be prepared.

The safety analysis will be performed on the safety population (SAF), which consists of all patients who underwent at least one enteroscopy.

Efficacy analyses will be based on the intent-to-treat (ITT) population, which includes all patients

- who underwent at least one enteroscopy and
- who had not major protocol deviations.

Note: Final decisions regarding validity will be made during the Review Meeting and documented in the Review Report (see Section 1.3).

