3.8 Other Analyses

None.

3.9 *List of all tables / listings / figures with their location in Clinical Study Report*

DT = Descriptive statistics table with n, mean, standard deviation, median, 25th and 75th percentiles, minimum and maximum

FT = Frequency table with absolute and relative frequencies, for the primary endpoint, 95% confidence intervals will be added

GL = General listing of parameters with patient ID, center, analysis population in each listing.

Description of table / figure / listing	Type
Tables	
11.1.1 Patient Disposition - All Enrolled Population Reference: annCRF page 5 Parameters: Patients with entries Analyses: absolute and relative frequencies	FT
11.1.2 Analysis Populations - All Enrolled Population Reference: None Parameters: Analyses populations (SAF, cSAF, ITT, cITT) Analyses: absolute and relative frequencies	FT
11.1.3 In- and Exclusion criteria fulfilled? - SAF and cSAF Reference: annCRF page 5-6 Parameters: Categorical parameters Analyses: absolute and relative frequencies	FT
11.1.4 Visit Schedules - SAF and cSAF Reference: annCRF Page 3 Parameters: Median time from enrollment to discharge Analyses: Descriptive analyses	DT
11.1.5.1 Demographics and Baseline Characteristics - Continuous Parameters - SAF and cSAF Reference: SAP chapter 3.5 Parameters: Age Analyses: Descriptive analyses	DT
11.1.5.2 Demographics and Baseline Characteristics - Categorical Parameters - SAF and cSAF Reference: SAP chapter 3.5 Parameters: Sex Analyses: absolute and relative frequencies	FT
11.1.6 Previous Abdominal Surgery - SAF and cSAF Reference: annCRF page 10-11 Parameters: Previous abdominal surgery, etc. Analyses: absolute and relative frequencies	FT
11.1.7.1 Information About Small-Bowel Enteroscopy - Listing of Indication - SAF and cSAF Reference: annCRF page 12 Parameters: Indication Analyses: Listing of freetext	GL
11.1.7.2 Information About Small-Bowel Enteroscopy - SAF and cSAF Reference: annCRF page 12 Parameters: Categorical parameters on information about planned small-bowel enteroscopy Analyses: absolute and relative frequencies	FT

Description of table / figure / listing	Type
11.1.7.3 Initially Planned Procedure with PowerSpiral - SAF and cSAF Reference: annCRF page 12-13 Parameters: Categorical parameters Analyses: absolute and relative frequencies	FT
11.1.7.4 Initially Planned Procedure with PowerSpiral - Listing of Freetext - SAF and cSAF Reference: annCRF page 12-13 Parameters: Freetext Analyses: Listing of freetext	GL

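### SAP 3.7.2 promises pre-treatment event tables, but SAP 3.1 bars never-scoped patients from all analyses, so such an event drops out exactly when it prevented any enteroscopy

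*SAP*

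**What the plan says.** The SAP makes a promise in one place and withdraws part of it in another.

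- SAP 3.7.2, after the special-interest counts: "For pre-treatment events summary tables and listings will be provided". It names no population and does not define pre-treatment.
- SAP 3.1: "All patients who did not undergo at least one enteroscopy will be considered as dropouts", followed by "Dropouts will be excluded from any statistical analyses". No exception is made for safety.
- SAP 3.1, on the widest safety set (SAF): it "will consist of all patients who underwent at least one enteroscopy including the training patients". The other three populations (cSAF, cITT, ITT) also require an enteroscopy.
- SAP 3.9: all adverse event tables, including special-interest Tables 11.3.1.8.1 and 11.3.1.8.2, are on SAF and cSAF (the subgroup table on cSAF only). No pre-treatment table or listing appears. All enrolled patients are used only for disposition and population counts, for example "11.1.1 Patient Disposition - All Enrolled Population".

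The protocol starts earlier. Section 3.3.4 sets enrolment at the signing of consent, and section 11.3.1 says: "After the signature on the consent form is obtained, any SAE occurring while the subject is enrolled in the study must be immediately reported". Section 1.2 shows why the time before insertion matters: "The prevailing complications of a deep enteroscopy are pancreatitis, perforation, bleeding and adverse events associated with sedation or anesthesia".

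**The concern.** A table of pre-treatment events should show what happened between consent and the procedure in everyone who consented. Under SAP 3.1, whether an event appears depends on what it led to. If the patient was scoped later, the event is eligible for the tables. If it ended the patient's only chance of an enteroscopy, the patient becomes a dropout and the event leaves with the patient. The events removed are those with the greatest consequence for the procedure.

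The special-interest count for sedation and anaesthesia has the same gap. A complication at induction that leads to permanent cancellation is not in SAF or cSAF, so it is not counted. Protocol 3.1.4 adds to this: a site keeps enrolling until it has 22 counting subjects, so the never-scoped patient is replaced in the denominator while the event is shown nowhere in the tables.

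At stake is the completeness of a descriptive safety profile in a registry whose stated purpose is to show safety in daily practice.

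**Working it through.** The point turns on text, so the main check follows individual cases through the rules.

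**Step 1. Which events stay in and which are lost.** The criterion is SAP 3.1: at least one enteroscopy.

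| Case | Enteroscopy performed? | In SAF? | Event eligible for AE tables? |
|---|---|---|---|
| Event between consent and V2, scoped as planned | yes | yes | yes |
| Event at induction, first procedure rescheduled and done (Protocol 3.4.3 sets no interval between V1 and V2) | yes | yes | yes |
| Event after scope insertion, procedure stopped | yes, on a natural reading | yes | yes |
| Event that prevents only the optional V3 | yes, at V2 | yes | yes |
| Event before insertion, never scoped | no | no (dropout) | **no** |

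Only the last row is affected, and its defining feature is the consequence of the event. The phrase in SAP 3.1 for having undergone an enteroscopy is not defined, so sedation without insertion, or an insertion abandoned at once, is left to the Review Meeting.

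**Step 2. Does any planned output catch the last row?** SAP 3.9 has no pre-treatment table or listing. Tables 11.1.1 and 11.1.2 cover all enrolled patients but contain no adverse events. SAP 3.7.2 also promises to report withdrawals due to adverse events. It names no population for this, SAP 3.1 does not exempt it, and a withdrawal count is not an event table.

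**Step 3. How many patients?** The documents do not say. The 5% drop-out allowance in Protocol 3.3.6 (260 × 0.05 = 13, or 260 − 245 = 15 from the stated evaluable number) is not an estimate of never-scoped patients. The protocol summary describes it as losses to follow-up, and Protocol 3.1.4 has sites replace subjects lost before the procedure.

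As an assumption only, take 1% to 5% of the roughly 335 enrolled:

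- 335 × 0.01 = 3.35, about 3 patients
- 335 × 0.05 = 16.75, about 17 patients

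How many of these would have an event is also unknown.

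**Step 4. Illustration of size (assumed counts).** Suppose there are 3 sedation complications among 260 scoped patients and 1 in a never-scoped patient. The plan reports 3/260 = 1.15%. Counting the fourth patient gives 4/261 = 1.53%. One of four events is missing, and the rate changes by about 0.4 percentage points.

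**The case against.** Several points on the other side are sound.

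- A safety set of treated patients is an ordinary choice, and nothing here requires SAF or cSAF to change.
- The loss is from the analysis tables, not from the record. SAEs are reported from consent, and the sponsor compiles an SAE list (Protocol 11.3.1.1).
- SAP 3.7.2 promises listings as well as tables, and a listing is arguably not a statistical analysis. Because the SAP already counts all enrolled patients in Tables 11.1.1 and 11.1.2, the specific promise could be read as surviving the general exclusion. That reading is possible, but the SAP does not state it and the output is not in SAP 3.9. For the same reason, those two tables are only weak evidence of a contradiction: showing who was excluded is their normal function.
- Protocol 4.1.3 says "The safety variables will be tabulated for all study participants". This is also weak support, because two of the three variables it refers to are tied to the enteroscopy itself.

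A reader might infer that an omitted event could turn a failed primary analysis into a pass. The arithmetic is easy to produce. The exact Clopper-Pearson method reproduces Table 1 of the protocol (10/245 gives 2.0% to 7.4%), and it gives an upper limit of 7.92% for 12/260 and 8.37% for 13/261, on either side of 8%. The documents do not support the inference. SAP 2.4 and 3.7.1 define the primary endpoint as SAEs during and after the enteroscopy, counted in cSAF. An SAE in a never-scoped patient is outside both the time window and the set, and the change proposed here leaves cSAF as it is.

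A reader might also infer that every event that stopped a procedure is lost, or that only mild pre-treatment events remain. Step 1 shows otherwise: a serious event that only delayed or interrupted a procedure stays in.

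**Conclusion.** The concern holds in a narrow form. As written, the promised pre-treatment tables omit an event exactly when it prevented the patient from ever being scoped, and the special-interest count for sedation and anaesthesia omits the same patients. The output is selected on the consequence of the event.

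The effect is confined to descriptive safety output; the primary endpoint and the 8% decision rule are untouched. Its size cannot be derived from the documents. The 3 to 17 never-scoped patients and the change from 1.15% to 1.53% rest on assumed inputs, and the true number of affected events may be zero. The conclusion assumes that the exclusion in SAP 3.1 is applied literally and that an enteroscopy means the scope was inserted.

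The text should be corrected before analysis, because the change is cheap and otherwise the handling of such patients is left to be settled at the Review Meeting.

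**What to change.** 1. In SAP 3.1, replace the exclusion sentence with: *Dropouts are not part of SAF, cSAF, ITT or cITT; they remain in the All Enrolled Population, on which Tables 11.1.1 and 11.1.2 and the pre-treatment event tables and listings (3.7.2) are produced.*
2. Define pre-treatment in SAP 3.7.2 as the time from consent to first scope insertion. This also settles the case of sedation without insertion.
3. Add the pre-treatment table and listing to SAP 3.9.
4. Keep the special-interest count on SAF and cSAF, and report sedation or anaesthesia complications in never-scoped patients on a separate line beside it. A rate over all sedated patients is not proposed as a replacement, because Protocol 3.4.2 records the type of sedation but lists no start time.

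The cost is SAP wording, one table and one listing, with no change to the sample size or the primary analysis. The descriptive safety profile may look slightly less favourable. The new output should carry a note on completeness: SAEs are reportable from consent, but Table 2 of the protocol marks adverse event collection only at V2 to V4, so non-serious events before V2 may be incomplete.

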3.7.3 Laboratory Data

Not applicable.

3.7.4 Vital Signs

Vital signs will be analyzed descriptively by visit including changes from baseline.

3.7.5 ECG Data

Not applicable.

3.7.6 Other Safety Data

Physical examination at baseline will be analyzed descriptively by summary tables. Listings will be provided.

3.8 Other Analyses

None.

3.9 *List of all tables / listings / figures with their location in Clinical Study Report*

DT = Descriptive statistics table with n, mean, standard deviation, median, 25th and 75th percentiles, minimum and maximum

FT = Frequency table with absolute and relative frequencies, for the primary endpoint, 95% confidence intervals will be added

GL = General listing of parameters with patient ID, center, analysis population in each listing.

Description of table / figure / listing	Type
Tables	
11.1.1 Patient Disposition - All Enrolled Population Reference: annCRF page 5 Parameters: Patients with entries Analyses: absolute and relative frequencies	FT
11.1.2 Analysis Populations - All Enrolled Population Reference: None Parameters: Analyses populations (SAF, cSAF, ITT, cITT) Analyses: absolute and relative frequencies	FT
11.1.3 In- and Exclusion criteria fulfilled? - SAF and cSAF Reference: annCRF page 5-6 Parameters: Categorical parameters Analyses: absolute and relative frequencies	FT
11.1.4 Visit Schedules - SAF and cSAF Reference: annCRF Page 3 Parameters: Median time from enrollment to discharge Analyses: Descriptive analyses	DT
11.1.5.1 Demographics and Baseline Characteristics - Continuous Parameters - SAF and cSAF Reference: SAP chapter 3.5 Parameters: Age Analyses: Descriptive analyses	DT
11.1.5.2 Demographics and Baseline Characteristics - Categorical Parameters - SAF and cSAF Reference: SAP chapter 3.5 Parameters: Sex Analyses: absolute and relative frequencies	FT
11.1.6 Previous Abdominal Surgery - SAF and cSAF Reference: annCRF page 10-11 Parameters: Previous abdominal surgery, etc. Analyses: absolute and relative frequencies	FT
11.1.7.1 Information About Small-Bowel Enteroscopy - Listing of Indication - SAF and cSAF Reference: annCRF page 12 Parameters: Indication Analyses: Listing of freetext	GL
11.1.7.2 Information About Small-Bowel Enteroscopy - SAF and cSAF Reference: annCRF page 12 Parameters: Categorical parameters on information about planned small-bowel enteroscopy Analyses: absolute and relative frequencies	FT

Description of table / figure / listing	Type
11.1.7.3 Initially Planned Procedure with PowerSpiral - SAF and cSAF Reference: annCRF page 12-13 Parameters: Categorical parameters Analyses: absolute and relative frequencies	FT
11.1.7.4 Initially Planned Procedure with PowerSpiral - Listing of Freetext - SAF and cSAF Reference: annCRF page 12-13 Parameters: Freetext Analyses: Listing of freetext	GL
11.1.7.5 Procedure with PowerSpiral - Categorical Parameters - SAF and cSAF Reference: annCRF page 16-17 Parameters: Procedure with PowerSpiral, Procedural information Analyses: absolute and relative frequencies	FT
11.1.7.6 Procedure with PowerSpiral - Continuous Parameters - SAF and cSAF Reference: annCRF page 16-17 Parameters: Length of procedure, Time to reach deepest point of enteroscopy, Time score out Analyses: descriptive statistics	DT
11.1.7.7 Therapeutic Interventions - Listing of Comments - SAF and cSAF Reference: annCRF page 17 Parameters: Freetext, Start and Stop time of intervention by patient Analyses: Listing of freetext	GL
11.2.1 Assessment After Procedure - Categorical Parameters - ITT and cITT Reference: annCRF page 18 Parameters: Categorical parameters Analyses: absolute and relative frequencies	FT
11.2.2 Assessment After Procedure - Listing of Comments - ITT and cITT Reference: annCRF page 18 Parameters: Freetext Analyses: Listing of freetext	GL
11.2.3 Evaluation of Procedure - Categorical Parameters - ITT and cITT Reference: annCRF page 19-20 Parameters: Handling, instrument insertion, Precision, time needed, staff and resources needed Analyses: absolute and relative frequencies by category (worse, similar, better)	FT
11.2.4 Evaluation of Procedure - Diagnostic Yield - ITT and cITT Reference: SAP section 3.6 Parameters: positive imaging prior to procedure, information whether a diagnosis was made with PSE Analyses: absolute and relative frequencies	FT

Description of table / figure / listing	Type
11.3.1.1 Adverse Events during procedure - SAF and cSAF Reference: annCRF page 17 Parameters: Trigger question on AEs Analyses: absolute and relative frequencies	FT
11.3.1.2.1 Adverse Events by category - SAF and cSAF Reference: annCRF page 23 Parameters: Adverse event category Analyses: absolute and relative frequencies	FT
11.3.1.2.2 Serious Adverse Events by category - SAF and cSAF Reference: annCRF page 23 Parameters: Adverse event category Analyses: absolute and relative frequencies	FT
11.3.1.3 Adverse Events by category - Listing of other AEs - SAF and cSAF Reference: annCRF page 23 Parameters: Freetext Analyses: Listing of Freetext	GL
11.3.1.4.1 Adverse Events - Relatedness - SAF and cSAF Reference: annCRF page 23 Parameters: Relatedness Analyses: absolute and relative frequencies	FT
11.3.1.4.2 Serious Adverse Events - Relatedness - SAF and cSAF Reference: annCRF page 23 Parameters: Relatedness Analyses: absolute and relative frequencies	FT
11.3.1.5 Adverse Events - Seriousness - SAF and cSAF Reference: annCRF page 23-24 Parameters: Seriousness and seriousness components (e.g. death) Analyses: absolute and relative frequencies	FT
11.3.1.6.1 Adverse Events - Actions taken - SAF and cSAF Reference: annCRF page 24 Parameters: Actions Analyses: absolute and relative frequencies	FT
11.3.1.6.2 Adverse Events - Listing of Actions taken - SAF and cSAF Reference: annCRF page 24 Parameters: Freetext Analyses: Listing of Freetext	GL

Description of table / figure / listing	Type
11.3.1.7.1 Adverse Events - Causality to PowerSpiral Device - SAF and cSAF Reference: annCRF page 24 Parameters: Causality Analyses: absolute and relative frequencies	FT
11.3.1.7.2 Serious Adverse Events - Causality to PowerSpiral Device - SAF and cSAF Reference: annCRF page 24 Parameters: Causality Analyses: absolute and relative frequencies	FT
11.3.1.7.3 Adverse Events - Listing of Comments on Causality to PowerSpiral Device - SAF and cSAF Reference: annCRF page 25 Parameters: Freetext Analyses: Listing of freetext	GL
11.3.1.8.1 Adverse Events - AEs of special interest - SAF and cSAF Reference: SAP section 3.7.2 Parameters: Frequency Analyses: absolute and relative frequencies	FT
11.3.1.8.2 Serious Adverse Events - AEs of special interest - SAF and cSAF Reference: SAP section 3.7.2 Parameters: Frequency Analyses: absolute and relative frequencies	FT
11.3.1.9 Subgroup analyses for the primary endpoint SAEs - cSAF Reference: SAP chapter 3.3 Parameters: SAEs by Subgroup Analyses: absolute and relative frequencies	FT
11.3.2.1 Hospital Discharge - Categorical Parameters - SAF and cSAF Reference: annCRF page 22 Parameters: Categorical parameters Analyses: absolute and relative frequencies	FT
11.3.2.2 Hospital Discharge - Listing of Comments - SAF and cSAF Reference: annCRF page 22 Parameters: Freetext Analyses: Listing of freetext	GL
11.3.3.1 Physical Examination by visit - Continuous Parameters - SAF and cSAF Reference: annCRF page 7-8 Parameters: Height, Weight, Heart Rate, Blood Pressure (RR), Diastolic blood Pressure Analyses: Measurement at each visit, change from baseline	DT
